#### 4.2.1.2 Myelodysplastic Syndrome

MDS comprises a heterogeneous group of malignant hematopoietic stem cell disorders characterized by dysplastic and ineffective blood cell production and a variable risk of transformation to acute leukemia. Patients often die of complications that arise from cytopenias or from subsequent AML. MDS occurs primarily in the elderly, with a median age of 72 years and male predominance. There are approximately 10,000 cases diagnosed annually in the United States [28]. However, a recent study indicates that the incidence may be as high as 45,000 cases per year, and potentially increasing with an aging population, which would make it the most common type of Heme malignancies [29]. MDS is classified using the World Health Organization (WHO) system based on morphology, immunophenotype, genetics and clinical feature into six entities: refractory cytopenia with unilineage dysplasia, refractory anemia with ringed sideroblasts, refractory anemia with multilineage dysplasia, refractory anemia with excess blasts, MDS with isolated del 5 and MDS, and unclassified [30]. Patients with untreated MDS are categorized into 4 IPSS prognostic risk groups: low, intermediate 1, intermediate 2 and high, which are associated with median survival times of 5.7, 3.1, 1.2, and 0.5 years, respectively [31]. Allogeneic stem cell transplantation (allo-SCT) from a human leukocyte antigen-matched sibling donor is a preferred approach for treating a selected group of patients with MDS, particularly those otherwise healthy patients with high-risk disease [32]. 5-azacytidine (5-Aza), and decitabine have been recently approved by the FDA for treating higher risk MDS patients. Despite these advances, the overall ORR with monotherapy of demethylating agents remains relatively low and the median survival reaches only about 2 years. Outcome after 5-Aza failure in high risk MDS is poor with a median OS of 5.6 months [33].

Aberrant up-regulation of PD-1, PD-L1, PD-L2, and CTLA4 expression has been demonstrated in peripheral blood mononuclear cells from MDS patients. This up-regulation is

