- d. In general, the window for each visit is ± 3 days unless otherwise noted.
- e. Written consent must be obtained prior to performing any protocol specific procedure. Results of a test performed prior to the subject signing consent as part of routine clinical management are acceptable in lieu of a screening test if performed within the specified time frame (e.g., within 28 days prior to the first dose of trial treatment). Screening number will be assigned when the study informed consent is signed.
- f. Signing the informed consent for future biomedical research (FBR) samples is optional. Detailed instructions for the collection and management of specimens for FBR are provided in the Procedures Manual and Section 12.2.
- g. Prior medications – Record all medications taken within 28 days of screening visit. Concomitant medications – Enter new medications started during the trial through the Safety Follow-up visit. Record all medications taken for SAEs as defined in Section 7.2.
- h. Transfusion history should be documented for 3 months prior to start of study and every 6 weeks during response assessment. Transfusion history should be obtained from subject medical records and/or blood bank records.
- i. AEs and laboratory safety measurements will be graded per NCI CTCAE version 4.0. All AEs, whether gradable by CTCAE or not, will also be evaluated for seriousness.
- j. Record all AEs occurring within 30 days after the last dose of trial treatment. Report all SAEs (related and unrelated to trial treatment) and ECIs occurring up until 90 days after the last dose of trial treatment or 30 days following cessation of treatment if the subject initiates new anticancer therapy, whichever is earlier. Afterwards, report only SAEs and ECIs that are related to trial treatment.
- k. To be repeated every 6 weeks after cycle 6.
- l. Vital signs to include temperature, pulse, respiratory rate, weight and blood pressure. Height will be measured at visit 1 only.
- m. Disease response assessment is made based upon the MDS response criteria and includes CBC and documentation of transfusions. Response assessments should occur at screening, Wk 6, Wk 12, and every 6 weeks (± 7 days). For subjects who discontinue for reasons other than PD, assessments should continue until the subject has documented PD. Bone marrow assessments should be performed at Screening, Wk 6 (± 7 days), Wk 12 (± 7 days), and then every 12 weeks or as clinically indicated.

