### 8.1.1 Efficacy Analyses

The FAS population (defined as all subjects with a baseline efficacy evaluation and at least one post-baseline efficacy evaluation) will serve as the primary population for the analyses of efficacy data in this trial. Supportive analyses of efficacy will be conducted in the intention to treat (ITT) population. An outline of the efficacy analysis strategy is presented in [Table 15](#) below. For Cohorts 1 thru 4, a 90% CI (two-sided) along with a one-sided p-value for testing the null hypothesis based on the binomial distribution will be provided for the rate in each cohort. The respective cohort is considered to have reached the efficacy objective if the corresponding one-sided p-value for testing the respective null hypothesis is less than 5%. For Cohort 5 (DLBCL), a 90% CI (two-sided) will be presented.

Table 15 Primary Analysis Strategy for Efficacy Endpoints

Endpoint/Variable (Description, Time Point)	Statistical Method	Analysis Population	Missing Data Approach
Primary 
 
1. MDS (Cohort 1): ORR based on IWG (2006 criteria for MDS (investigator-assessed)
 
2. MM (Cohort 2): ORR based on IMWG criteria (investigator-assessed)
 
3. HL (Cohort 3): Complete Remission Rate (CRR) based IWG criteria (investigator-assessed)
 
4. NHL monotherapy (Cohort 4): ORR based on IWG criteria (investigator-assessed)
 
5. NHL combination therapy (Cohort 5): ORR based on IWG criteria (investigator-assessed)
 
	Exact test of binomial parameter (Cohorts 1 thru 4); Descriptive statistics (Cohort 5)	FAS	Subjects with missing data are considered non-responders

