Secondary binary endpoints 
 
• MDS (Cohort 1):                     
 
a. Bone marrow response by IWG criteria (investigator assessed)
 
b. Hematologic improvement by IWG criteria (investigator-assessed)
 
c. Cytogenetic response by IWG criteria (investigator assessed)
 
 
 
• MM (Cohort 2):                     
 
a. CR + sCR by IMWG criteria (investigator assessed)
 
 
 
• HL (Cohort 3):                     
 
a. ORR
 
 
 
• NHL monotherapy (Cohort 4): none
 
• NHL combination therapy (Cohort 5): none
 
	Exact test of binomial parameter	FAS	Subjects with missing data are considered non-responders

Endpoint/Variable (Description, Time Point)	Statistical Method	Analysis Population	Missing Data Approach
Secondary time-to-event endpoints 1. MDS (Cohort 1): a. OS b. DOR 2. MM (Cohort 2): a. TTP b. DOR c. PFS d. OS 3. HL (Cohort 3): a. PFS b. OS c. DOR 4. NHL monotherapy (Cohort 4): a. PFS b. OS c. DOR 5. NHL combination therapy (Cohort 5): a. PFS b. OS c. DOR	Summary statistics using Kaplan-Meier method	OS, TTP, PFS: FAS DOR: all responders	Censored at last assessment
Secondary descriptive analyses Response by PD-L1 expression change before and after HMA treatment in each population separately: 1. MDS (Cohort 1) 2. MM (Cohort 2) 3. HL (Cohort 3) 4. NHL monotherapy (Cohort 4) 5. NHL combination therapy (Cohort 5)	Descriptive statistics	FAS	

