#### **8.2.4 Analysis Populations**

##### **8.2.4.1 Efficacy Analysis Populations**

The FAS population will serve as the primary population for the analysis of efficacy data in this study. The FAS population consists of all randomized subjects in each disease cohort who:

- Receive at least one dose of study treatment,
- Have a baseline disease assessment, and
- Have a post baseline disease assessment OR discontinue the trial due to PD/drug related AE

Supportive analyses will be conducted in the ITT population, defined as all randomized subjects.

For MDS cohort only, two additional subpopulations FAS/WHO-Classification and ITT/WHO-Classification will be used. These two populations have the same definition as above except for requiring the baseline disease assessment to satisfy WHO criteria.

Subjects will be included in the treatment group to which they are randomized for the analysis of efficacy data. Details on the approach to handling missing data are provided in Section 8.2.5 Statistical Methods.

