Secondary time-to-event endpoints 1. MDS (Cohort 1): a. OS b. DOR 2. MM (Cohort 2): a. TTP b. DOR c. PFS d. OS 3. HL (Cohort 3): a. PFS b. OS c. DOR 4. NHL monotherapy (Cohort 4): a. PFS b. OS c. DOR 5. NHL combination therapy (Cohort 5): a. PFS b. OS c. DOR	Summary statistics using Kaplan-Meier method	OS, TTP, PFS: FAS (P) ITT (S) DOR: all responders	Censored at last assessment
Secondary descriptive analyses Response by PD-L1 expression change before and after HMA treatment in each population separately: 1. MDS (Cohort 1) 2. MM (Cohort 2) 3. HL (Cohort 3) 4. NHL monotherapy (Cohort 4) 5. NHL combination therapy (Cohort 5)	Descriptive statistics	FAS (P) ITT (S)	

P=Primary approach; S=Supportive approach; FAS=Full Analysis Set; ITT=Intention to treat

In addition to the analyses specified above for overall cohort 4, separate efficacy analyses, descriptive in nature, will be performed with subjects with relapsed / refractory MLBCL (Cohort 4A), FL (Cohort 4C + FL subjects in Cohort 4B), DLBCL (Cohort 4D + DLBCL subjects in Cohort 4B), and Other (Cohort 4B excluding FL and DLBCL subjects).

The strategy to address multiplicity issues with regard to multiple efficacy endpoints is described in Section 8.2.6, Multiplicity and Section 8.2.9, Interim Analyses.

Exploratory objectives in each cohort will be evaluated using descriptive statistics.

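### The primary OS and PFS analyses use the FAS, so a treated subject who dies of another cause before any post-baseline assessment is left out of the curve

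*Combined protocol and SAP*

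**What the plan says.** Table 17 (Section 8.2.5.1) assigns the analysis sets for the secondary time-to-event endpoints as "OS, TTP, PFS: FAS (P) ITT (S) DOR: all responders", where P is the primary and S the supportive approach. The matching row of Table 15 (Section 8.1.1) reads "OS, TTP, PFS: FAS DOR: all responders".

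The FAS is defined twice, and the definitions differ:

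- Section 8.1.1: "defined as all subjects with a baseline efficacy evaluation and at least one post-baseline efficacy evaluation".
- Section 8.2.4.1: at least one dose, a baseline assessment, and a third condition, "Have a post baseline disease assessment OR discontinue the trial due to PD/drug related AE".

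Death is not a route into the set under either definition. The missing-data rule for these endpoints is censoring at the last assessment, which can act only on subjects already in the set. On ITT, Section 8.2.4.1 adds: "Supportive analyses will be conducted in the ITT population, defined as all randomized subjects". Allocation here is non-random, so this means all allocated subjects.

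For Cohort 1, footnote m of Flow Chart A (Section 6.1) sets the schedule: "Response assessments should occur at screening, Wk 6, Wk 12, and every 6 weeks". Table 10 (Section 7.1.2.7.4) puts the first assessment at Week 12 for HL/NHL subjects on Q2W dosing and for Cohort 5.

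**The concern.** Membership of the FAS is settled after treatment starts. A subject treated on Day 1 who dies of infection or bleeding in Week 4, with no assessment and nothing recorded as PD or drug-related AE, does not qualify. For a response rate this is a question of denominator. For OS and PFS it removes the event being measured, while everyone who lives to an assessment is kept with that survival time credited. The curve then partly describes survival among subjects who reached an assessment, not survival of the treated cohort. OS needs no disease assessment at all, because survival status is collected by telephone.

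Such deaths are foreseeable. Section 4.2.1.2 says of MDS: "Patients often die of complications that arise from cytopenias or from subsequent AML". OS is a listed secondary endpoint in every cohort and PFS in Cohorts 2 to 5. With no control arm, a reader has little except background survival figures to set the curves against.

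**Working it through.** **The plan's own figures.** The SAP gives no sample size, event count or power for OS, PFS or TTP, so there is nothing to reproduce for these endpoints. The nearest figure tied to the FAS is the MDS/HL response rule of at least 6/25. The exact binomial gives type I error 0.033 at 10% and power 0.807 at 30%, which agrees with the stated ~80%. This point does not touch that rule.

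**Direction.** Take one subject with a death at time t out of a Kaplan-Meier data set. From t onward the estimate can only rise: the drop at t is smaller, later risk sets are unchanged, and the slightly smaller earlier risk sets do not offset this.

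**Size, as an illustration.** Inputs from the documents:

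- MDS: "Outcome after 5-Aza failure in high risk MDS is poor with a median OS of 5.6 months" (Section 4.2.1.2); first assessment at Week 6.
- MM: OS of 9 months (Section 4.2.1.4), read here as a median; first assessment at Week 4 on Q2W.
- HL: about 1.2 years = 14.4 months (Section 4.2.1.3); first assessment at Week 12.

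Assumptions: exponential survival with median m, and the first scheduled assessment at L months as the cut. A fraction f of the deaths before L is excluded. The documents do not give f, so it is shown as a range.

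Share dying before L: p = 1 − 2^(−L/m). After L the curve becomes S(t)/(1 − f·p), so the median is m × [1 − log2(1 − f·p)].

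MDS: L = 6 × 7 × 12/365.25 = 1.38 months, and p = 1 − 2^(−1.38/5.6) = 0.157, or 3.9 of 25 subjects. At f = 0.25, f·p = 0.039 (1.0 subject) and the median is 5.6 × [1 − log2(0.961)] = 5.92 months.

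| Cohort | m (months) | p | f = 10% | f = 25% | f = 50% | f = 100% |
|---|---|---|---|---|---|---|
| MDS, Week 6 | 5.6 | 15.7% | 5.73 | 5.92 | 6.26 | 6.98 |
| MM Q2W, Week 4 | 9.0 | 6.8% | 9.09 | 9.22 | 9.45 | 9.92 |
| HL, Week 12 | 14.4 | 12.4% | 14.66 | 15.06 | 15.73 | 17.16 |

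The last column is the literal Section 8.1.1 definition. Section 8.2.4.1 corresponds to some smaller f. As a check, full exclusion under an exponential model shifts the median by exactly L: 5.6 + 1.38 = 6.98. Twelve-month OS in MDS moves from 22.6% to 23.6% at f = 25% and to 26.9% at f = 100%.

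**Scale against sampling error.** With 25 uncensored exponential subjects the asymptotic standard error of the median is m/(ln 2 × √25) = 5.6/(0.693 × 5), about 1.6 months. The shifts at f = 25% and 50% are 0.3 and 0.7 months.

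**The case against.** Several points against the concern are sound.

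- **More routes into the set.** Section 8.2.4.1 keeps subjects who discontinue for PD or a drug-related AE. The flow charts ask for an assessment at discontinuation when progression is not confirmed (for example Section 6.1 note o, Section 6.2 note p, Section 6.3 note p). Lymphoma scans may come before Week 12 if the subject is clinically progressing. This leaves mainly subjects who die on treatment, or too soon for an assessment, of a cause not recorded as PD or drug-related AE. The MDS response table in Section 12.7.1 classes death during treatment as failure. That could be read as a post-baseline outcome, but the FAS text does not say so.
- **Entry criteria.** Cohort 1 requires expected survival long enough to assess response, and the lymphoma cohorts require life expectancy over 3 months.
- **Background medians.** The 5.6 months is for high-risk MDS after azacitidine failure, while Cohort 1 also takes Intermediate-1 and Intermediate-2 disease. The 1.2 years is for HL relapsing or progressing within a year of autologous transplant, while Cohort 3 also admits transplant-ineligible subjects and those who refused transplant. The table is therefore more likely high than low.
- **ITT is planned.** Table 17 lists it for this row. Section 8.1.1 commits to it in the text introducing Table 15, and that table is titled as the primary strategy only. A reader might infer from Table 15 that no ITT survival analysis exists, and that would be wrong.
- **Low stakes.** These are descriptive Kaplan-Meier summaries. No historical OS or PFS comparison is planned, Table 18 gives response rates only, and Section 8.1 allows the analyses of Cohorts 2 and 5 to be modified.

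All of this limits the size. None of it gives a reason for the headline OS and PFS estimates to come from a set whose membership depends on surviving to an assessment, when two sets without that condition are already defined.

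**Conclusion.** The point stands in a limited form. The primary OS and PFS curves omit any treated subject who dies before a post-baseline assessment of a cause not recorded as PD or drug-related AE, and omitting those deaths can only raise the later curve. How many subjects this affects is unknown and probably few. On the MDS illustration the median of 5.6 months becomes about 5.7, 5.9 or 6.3 months if 10%, 25% or 50% of deaths before Week 6 are left out. This rests on exponential survival, the high-risk median and an assumed excluded share.

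A reader might infer that all early deaths leave the curve, so that median OS is inflated by about 25% in MDS (5.6 to 7.0 months) and 19% in HL (14.4 to 17.2 months). The documents do not support that as an expected size. It needs every early death to be excluded, which only Section 8.1.1 implies, and it uses medians from poorer-prognosis groups than those enrolled. These figures are upper bounds. Nor is an upward bias shown for TTP, because the SAP does not define how deaths count in it.

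No type I error, formal test or primary response conclusion is affected. This is a cheap improvement, not a flaw that threatens the trial's main results.

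**What to change.** In Tables 15 and 17, make all treated subjects (ASaT, already defined in Section 8.2.4.2) or the already planned ITT set primary for OS and PFS. Keep ITT in the row in either case, and list the FAS as supportive. TTP may use the same set for consistency. Leave DOR in responders.

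State that a death before the first assessment is an OS and PFS event at the date of death, and that an event-free subject with no post-baseline assessment is censored at Day 1 for PFS. Use a single FAS definition in Sections 8.1.1 and 8.2.4.1. Leave the response-rate populations unchanged.

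The cost is one row in each of two tables, a short event and censoring rule, one aligned definition, and a rerun of the same Kaplan-Meier program. It needs no new data, visits or subjects. The downside is that reported OS and PFS may be slightly less favourable.

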### **8.2.5.2 Statistical Methods for Safety Analyses**

Safety and tolerability will be assessed by clinical review of all relevant parameters including AEs, laboratory tests, and vital signs.

Summary statistics (counts, percentage, mean, standard deviation, etc.) will be provided for the safety endpoints as appropriate. The 95% CI for the incidence rate of Grade 2 or higher adverse events with an immune etiology and the incidence rate of Grade 4/5 AEs will be provided as appropriate.

Safety analysis will be performed separately for Cohorts 1 through 5 as well as the subtypes within Cohort 4.

### **8.2.5.3 Summaries of Baseline Characteristics, Demographics, and Other Analyses**

#### **8.2.5.3.1 Demographic and Baseline Characteristics**

Baseline characteristics will be assessed by the use of tables and/or graphs for each cohort. No statistical hypothesis tests will be performed on these characteristics. The number and percentage of subjects screened, randomized, the primary reasons for screening failure, and the primary reason for discontinuation will be displayed. Demographic variables (e.g., age, gender), baseline characteristics, primary and secondary diagnoses, and prior and concomitant therapies will be summarized by treatment either by descriptive statistics or categorical tables.

### **8.2.6 Multiplicity**

The false positive rate for testing the primary efficacy endpoint in each disease cohort (MDS, MM, HL, and NHL monotherapy is controlled at 0.05 (1-sided) for each cohort. No additional multiplicity adjustment is required because each disease cohort will be evaluated independently. No statistical testing will be performed for Cohort 5 (NHL combination therapy).

### **8.2.7 Sample Size and Power Calculations**

The calculation of power and sample size for each cohort does not account for an interim analysis.

#### **MDS (Cohort 1)**

With approximately 25 subjects with intermediate-1, intermediate-2, or high risk MDS, the study has ~80% power to detect a 20% difference in ORR under the null hypothesis of ORR=10% with a one-sided type I error rate of 5% if the true ORR is 30%. Success for this hypothesis requires at least 6/25 responses. The null hypothesis ORR of 10% is based on the historic response rate in phase I/II trials of chemotherapy in MDS ([Table 18](#)). The actual number of subjects enrolled may be larger than 25 to ensure that at least 25 subjects are evaluable for analysis.

## **MM (Cohort 2)**

With approximately 28 subjects with MM, the study has ~80% power to detect a 25% difference in ORR under the null hypothesis of ORR=25% with a one-sided type I error rate of 5% if the true ORR is 50%. Success for this hypothesis requires at least 12/28 responses. The null hypothesis ORR of 25% is based on the historic OR rate for MM ([Table 18](#)). The actual number of subjects enrolled may be larger than 28 to ensure that at least 28 subjects are evaluable for analysis.

## **Lymphoma – HL (Cohort 3)**

With approximately 25 subjects with HL, the study has ~80% power to detect a 20% difference in CRR under the null hypothesis of CRR=10% with a one-sided type I error rate of 5% if the true CRR is 30%. Success for this hypothesis requires at least 6/25 responses. The null hypothesis CRR of no greater than 10% is estimated based on CR rate observed in prior studies of single agents in relapsed / refractory HL combined with the assumption that the HL population enrolled in the current trial would have failed prior brentuximab vedotin treatment ([Table 18](#)). The actual number of subjects enrolled may be larger than 25 to ensure that at least 25 subjects are evaluable for analysis.

Table 18      Historic Response Rates for Hematologic Malignancies

Disease	Reference	Agents	N	Response rate	Timing of Response Assessment
MDS	Bhatnagar [91]	Decitabine	13	0% ORR	Best objective response
	Silverman [92]	5-Aza	191	23% ORR	Best objective response
MM	Siegel [93]	Carfilzomib	257	23.7%	Best objective response
	Richardson [94]	Pomalidomide w/ low-dose Dexamethasone	113	33%	Best objective response
HL	Devizzi [95]	Vinorelbine	22	14% CR	Best objective response
	Savage [96]	Gemcitabine	29	0% CR	Best objective response
	Younes [39]	Brentuximab	102	34% CR	Best objective response
NHL	Churpek [97]	Epothilone	51	27% ORR	Best objective response
	Goy [98]	Bortezomib	27	19%	Best objective response
	Wiernik [54]	Lenalidomide	49	35%	Best objective response

## **Lymphoma –NHL monotherapy (Cohort 4)**

With approximately 78 subjects with NHL, the study has ~80% power to detect a 14% difference in ORR under the null hypothesis of ORR=25% with a one-sided type I error rate of 5% if the true ORR is 39%. Success for this hypothesis requires at least 27/78 responses. The null hypothesis ORR of 25% is based on the historic OR rate from chemotherapy trials in NHL and MLBCL ([Table 18](#)). The actual number of subjects enrolled may be larger than 78 to ensure that at least 78 subjects are evaluable for analysis.

The maximum half-width of the 2-sided 90% exact CI will be 16% for the DLBCL and FL subtypes with a targeted number of 30 subjects each, and wider CIs for the MLBCL and Other subtypes.

